9.5. Analyses of Exploratory Efficacy Endpoints

9.5.1. Rate of All Laboratory-confirmed Viral Infections with or without Symptoms

The rate of all laboratory-confirmed viral infections with or without symptoms beginning at least 3 days after the start of study drug treatment through Week 16 as assessed by respiratory pathogen PCR of nasopharyngeal swabs and/or RIDTs (obtained during episodes of clinically symptomatic respiratory illnesses) and/or respiratory pathogen PCR of mid-turbinate swabs (obtained at required clinical visits even in the absence of symptoms) will be analyzed in the same manner as described in [9.4.2 above](#).

All positive results from specimens (respiratory pathogen PCR of nasopharyngeal swabs or midturbinate swabs and/or RIDT) collected at least 3 days after the start of study drug treatment through Week 16, which may or may not be associated with a CSRI, will count as laboratory-confirmed viral infections (both symptomatic and asymptomatic).

This document is confidential.

Summary statistics will be presented along with a full data listing by treatment group.

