and 8) for the first 8 weeks, and then every 4 weeks (visit Week 12 and 16) for the final 8 weeks. At visit Weeks 2-12 of the study, the subject will have clinical evaluations, including a targeted physical exam, which will include measurements of weight, blood pressure, heart rate, respiratory rate, and temperature, and an exam of the lungs, heart, oral cavity, and skin. A review of any changes to medical (including cardiac) conditions and medications/other therapies will also be performed. At all follow up visits, subjects will be queried by site staff regarding any visits to the ER, urgent care clinics, and any admission to a skilled nursing facility or hospital that may have occurred since their last study visit. Subjects will also have a mid-turbinate swab taken at each visit regardless of whether the subject reports respiratory illness symptoms. If subject presents with respiratory illness symptoms at this visit they may also have a nasopharyngeal swab, RIDT and sputum sample (if applicable) obtained as part of an unscheduled visit assessment. Blood and urine specimens will be collected at each visit for safety monitoring. An ECG will be performed at Week 4, 8 and 12 visits for safety monitoring. Only subjects participating in the PK assessments (per the Interactive Web or Telephone-based Response System (IXRS) randomization) will also have blood samples obtained for PK assessments at the Week 4 (or 6 if applicable), 8, and 12 visits, and have blood samples obtained for RNA expression and soluble biomarker assessments at the Week 4 visit. If PK sampling cannot be performed at the Week 4 visit for logistical reasons, it should be collected at the Week 6 visit instead, but according to the schedule described below for Week 4. This applies to the timing of the biomarker specimens originally scheduled for Week 4 as well.

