An exploratory endpoint will be the rate of viral respiratory infection, irrespective of whether the infection is symptomatic, to better assess the antiviral effects of RTB101. As an additional exploratory endpoint, healthcare resource utilization will be assessed because an important benefit of decreasing the incidence of clinically symptomatic respiratory illness may be a decrease in healthcare resource utilization by elderly subjects. Since decreasing the incidence of clinically symptomatic respiratory illness may improve the quality of life of elderly subjects, an

additional exploratory endpoint will be health related quality of life in all subjects assessed with the EQ-5D-5L questionnaire. The incidence of clinically symptomatic respiratory illness in subjects with a medical history of asthma or who are ≥ 85 years of age will be assessed as exploratory endpoints because these subpopulations had the greatest reduction on the incidence of laboratory confirmed RTIs after treatment with 10 mg RTB101 once daily as compared with placebo in the previous Phase 2b (RTB-BEZ235-202) trial. The incidence of asthma exacerbations in subjects with a medical history of asthma will also be assessed since RTIs are common causes of asthma exacerbations. Another exploratory endpoint will be the incidence of clinically symptomatic respiratory illness and the incidence of symptomatic respiratory illness associated with laboratory-confirmed pathogen(s) through Week 20 to assess if the efficacy of RTB101 persists for 4 weeks after subjects discontinue study drug. To better understand if the incidence of other types of infections may be reduced, the incidence of UTIs will be assessed. Finally, RNA expression and soluble serum biomarkers and pharmacogenomics (also known as pharmacogenetics) (Note: pharmacogenomics will only be assessed in those subjects who sign a separate consent form to allow collection of a pharmacogenomic (also known as pharmacogenetic) sample) will be assessed as exploratory endpoints to assess the effects of RTB101 on relevant immunologic markers and to potentially assess the impact of mTOR pathway polymorphisms in a pharmacogenomic analysis.

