- Review of prior and concomitant medications including dates of the most recent administration (if applicable) of the pneumococcal and the current seasonal influenza vaccinations.
- Clinical evaluation, including a targeted physical exam to include measurements of weight, orthostatic blood pressure, heart rate, respiratory rate, and temperature, and an exam of the lungs, heart, oral cavity, and skin.
- Clinical frailty index score assessment (see [Section 13.4](#) [Appendix 4]).
- ECG for Baseline safety assessment.
- A mid-turbinate swab will be obtained.
- Blood and urine samples obtained for Baseline safety assessments.
- Blood samples will be obtained for biomarker (including RNA expression and soluble serum biomarker) analysis.
- Blood samples will be obtained for potential future pharmacogenomic assessments (for consenting subjects only).
- Once randomized via IXRS, subjects will be administered their first dose of study drug at the study site. Subjects will be instructed on how to complete the dosing and the Respiratory Illness Symptom Questionnaire in the eDiary daily at home. Subjects will then complete the Health Related Quality of Life (EQ-5D-5L; see [Section 13.3](#)

[Appendix 3]) and Respiratory Illness Symptom Questionnaire on their eDiary at the Baseline visit.

After assessment for adverse events, subjects will then be sent home with study drug and the eDiary. Subjects will be instructed to take study drug at home daily with breakfast and to bring remaining study drug to all study visits.

Provided the study drug continues to be well tolerated, subjects will be treated with study drug through the Week 16 Visit, during which time they will return to the clinic every 2 weeks (Visits Week 2, 4, 6, and 8) for the first 8 weeks, and then every 4 weeks (Visits Week 12 and 16).

Week 2 Visit:

Subjects will return to the study site 2 weeks after starting study drug. The following evaluations will be performed:

- Review of interim and current medical (including cardiac) conditions (see SOM for details).
- Clinical evaluation, including a targeted physical exam to include measurements of weight, blood pressure, heart rate, respiratory rate, and temperature, and an exam of the lungs, heart, oral cavity, and skin.
- Assessments for safety including any adverse/serious adverse events and any concomitant medications taken since the last study visit.

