- Subjects will have a mid-turbinate swab taken. If a subject presents with respiratory illness symptoms at this visit they may also have a nasopharyngeal swab, RIDT and sputum sample (if applicable) as outlined in the unscheduled visit assessments.
- Subjects will complete the Health Related Quality of Life (EQ-5D-5L).
- Remaining study drug will be returned. No study drug will be dispensed as this will be end of treatment.

Week 20 Visit: End of the Short-term Follow-up Period of the Study

All subjects will be followed up for 4 weeks after their last dose of study drug. The following evaluations will be performed:

- Review of interim and current medical (including cardiac) conditions (see SOM for details).
- Clinical evaluation, including a complete physical exam to include measurements of weight, blood pressure, heart rate, respiratory rate, and temperature.
- If a subject presents with respiratory illness symptoms at this visit they may also have a nasopharyngeal swab, RIDT and sputum sample (if applicable) obtained as outlined in the unscheduled visit assessments (section 3.1).
- Assessments for safety including any adverse/serious adverse events and any concomitant medications taken since the last study visit.
- Obtain information about whether subjects have been evaluated in an ER or urgent care facility or been admitted to a hospital or skilled nursing facility since their last visit.
- Blood and urine samples will be obtained for safety assessments.
- eDiaries will be returned.

Subject who have AEs that are continuing at the end of the Short-term Follow-up Period (i.e., Week 20 Visit) will be captured as “ongoing” in the database; however, the AEs should continue to be followed until resolution or judged to be permanent by the Investigator (see [Section 7.1](#)).

Clinically Symptomatic Respiratory Illness Unscheduled Visits

Refer to [Section 3.1](#).

Week 48: End of the Long-term Follow-up Period of the Study

As part of extended long-term safety follow-up post-treatment, sites will contact subjects by telephone at Week 48 to capture information on a questionnaire concerning hospitalization(s), skilled nursing facility admission(s) and deaths that have occurred since the Week 20 visit.

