¹¹ All subjects will be administered their first dose of study drug at the site at the Baseline Visit. Approximately 400 subjects (per IXRS randomization) will be required to undergo PK assessment in the study (~ 200 from each treatment arm). For subjects participating in the PK analysis for the study, at the Week 4 (or Week 6 if applicable) and Week 12 study visits, study drug should not be taken at home and instead study drug will be administered together with a light meal at the study site following the pre-dose PK draw. If PK sampling cannot be performed at the Week 4 visit for logistical reasons, it should be collected at the Week 6 visit instead, but according to the schedule described above for Week 4. This applies to timing of biomarker samples originally scheduled for Week 4 as well.

^{12a} Subject will be given a personal tablet device containing the eDiary and instructions on use at this visit.

^{12b} The personal tablet device containing the eDiary will be collected from the subject at this visit.

¹³ Health Related Quality of Life (EQ-5D-5L) to be completed by all subjects at Baseline and Week 16, and each day that they report experiencing one or more respiratory illness symptoms through Week 20.

¹⁴ Nasopharyngeal swabs for respiratory pathogen PCR is to be done during a scheduled or an unscheduled visit for all subjects who report at least one unique respiratory symptom (runny nose, sneezing, stuffy nose, sore throat, hoarseness, or cough) on 2 consecutive entries in their eDiary. The swabs should be obtained if they are able to within 48 hours of 2 consecutive eDiary entries of one or more unique respiratory symptoms. Subjects who record at least 1 respiratory symptom and at least 1 general (headache, feverishness/chills or loss of appetite) symptom, both of which are moderate or severe on two consecutive days in their eDiary, should be brought in within 24 hours of the second day of eDiary symptom entry. Subjects who are unable to come to the study site may also have the nasopharyngeal swab (and, if indicated, a sputum specimen and RIDT) obtained during a home visit by trained personnel. Only one nasopharyngeal swab should be obtained during each episode of respiratory illness. Nasopharyngeal swabs will be collected through Week 20, see the SOM for more details.

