9.4. Analyses of Secondary Efficacy Endpoints

9.4.1. Percentage of Subjects with One or More Clinically Symptomatic Respiratory Illnesses Associated with ≥ 1 Laboratory-confirmed Pathogen(s)

The percentage of subjects with CSRI associated with ≥ 1 laboratory-confirmed pathogen(s) beginning at least 3 days after the start of study drug treatment through Week 16 (H_2) as assessed by pre-specified clinical diagnostic criteria and respiratory pathogen PCR of nasopharyngeal swabs, sputum gram stain and culture, and/or RIDTs will be analyzed in the same manner as the primary efficacy analysis as described in 9.3.1 based on the estimand for the secondary objective corresponding to this endpoint described in 9.2.2 above.

Laboratory results from a specimen obtained within 3 days before the CSRI start date through the CSRI end date will be used to determine if the CSRI is associated with ≥ 1 laboratory-confirmed pathogen. Laboratory confirmation includes a positive respiratory pathogen PCR of nasopharyngeal swabs, sputum gram stain and culture, and/or RIDT. If multiple specimens are obtained for a particular CSRI, then any positive result will be counted as laboratory confirmation if it occurs within 3 days before the CSRI start date through the CSRI end date. A laboratory-confirmed CSRI may be associated with multiple pathogens. Note that organisms considered to identify a positive sputum specimen should meet standard microbiological laboratory criteria of growing from a sputum specimen with > 25 WBC/hpf and < 10 Squamous cells/ hpf, and they have matching morphology on gram stain and culture.

Summary statistics will be presented along with a full data listing by treatment group.

9.4.2. Rate of Clinically Symptomatic Respiratory Illnesses (with or without an Associated Laboratory-confirmed Pathogen)

The rate of CSRI (with or without an associated laboratory-confirmed pathogen) beginning at least 3 days after the start of study drug treatment through Week 16 (H_3) will be analyzed based on the negative binomial distribution. The first 3 days of study drug treatment will not be included in determining the denominator of rate.

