A generalized linear model analysis will be conducted using the number of CSRI per 16-week period (illnesses/16 weeks) as the dependent variable and will include treatment group, age (continuous covariate), Clinical Frailty Scale score (ordinal covariate), medical history of diabetes mellitus type 2 (Y/N), medical history of asthma (Y/N) medical history of CHF (Y/N), and receipt of current season influenza vaccination (Y/N) as fixed effects.

This document is confidential.

The rate ratio (RR) (RTB101 dose group to placebo) of the treatment effect will be derived from the model along with the 95% 2-sided confidence interval (CI). Model-adjusted mean rates for each treatment group and their corresponding 95% 2-sided CI will also be calculated.

The “log” link function will be used in the model and an offset term will be included to account for variable lengths of treatment exposure across the subjects. The unadjusted rate of CSRI per subject through Week 16 will be calculated by summing the number of total CSRIs per subject through Week 16 within each treatment group.

Analysis of this endpoint will be based on the estimand for the secondary objective corresponding to this endpoint described in 9.2.2 above.

Summary statistics will be presented along with a full data listing by treatment group.

9.4.3. Rate of Clinically Symptomatic Respiratory Illness Associated with ≥ 1 Laboratory-confirmed Pathogen(s)

The rate of CSRIs associated with ≥ 1 laboratory-confirmed pathogen(s) beginning at least 3 days after the start of study drug treatment through Week 16 (**H₄**) as assessed by pre-specified clinical diagnostic criteria and respiratory pathogen PCR of nasopharyngeal swabs, sputum gram stain and culture, and/or RIDTs will be analyzed in the same manner as described in 9.4.2 above, based on the estimand for the secondary objective corresponding to this endpoint described in 9.2.2 above. Section 9.4.1 describes which laboratory result will be used to determine if the CSRI is associated with ≥ 1 laboratory-confirmed pathogen.

Summary statistics will be presented along with a full data listing by treatment group.

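### The rate of all viral infections with or without symptoms (SAP 9.5.1) pools symptom-triggered and scheduled swabs, so a drug that moved infections below the swab trigger without preventing any would give a rate ratio below 1.

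*SAP*

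**What the plan says.** Protocol Section 3.2 gives the purpose of the endpoint: "An exploratory endpoint will be the rate of viral respiratory infection, irrespective of whether the infection is symptomatic". It is meant to give a better view of the antiviral effect.

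There are two routes to a positive result.

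- **Triggered.** Under footnote 14 of Protocol Table 6-1, the nasopharyngeal PCR swab "is to be done during a scheduled or an unscheduled visit for all subjects who report at least one unique respiratory symptom" on two consecutive eDiary entries. No severity threshold applies. Rapid influenza tests also depend on symptoms.
- **Scheduled.** For the visits at Weeks 2 to 12, Protocol Section 3.1 says "Subjects will also have a mid-turbinate swab taken at each visit regardless of whether the subject reports respiratory illness symptoms". For Week 16, Protocol Section 6 says "Subjects will have a mid-turbinate swab taken". Section 6 gives the timetable as "Visits Week 2, 4, 6, and 8) for the first 8 weeks, and then every 4 weeks (Visits Week 12 and 16". That makes six post-baseline swabs, 14 days apart up to Week 8 and 28 days apart after it.

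SAP 9.5.1 pools both routes. The rate using triggered specimens and "mid-turbinate swabs (obtained at required clinical visits even in the absence of symptoms) will be analyzed in the same manner as described in" Section 9.4.2 is a negative binomial analysis with a log link. In that model "an offset term will be included to account for variable lengths of treatment exposure across the subjects", and "The first 3 days of study drug treatment will not be included in determining the denominator of rate". The second paragraph of 9.5.1 counts every positive specimen from Day 3 to Week 16, whether or not it belongs to a CSRI. Unlike 9.4.6, Section 9.5.1 does not rule out formal testing or p-values.

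**The concern.** An infection that meets the trigger is watched for every day. One that does not can be found only if a scheduled visit happens to fall while the virus is detectable. The probability of being counted therefore depends on symptoms. Symptoms are something the sponsor expects the drug may alter: the severity and duration of symptoms are secondary endpoints (H5 and H6). Randomisation and blinding do not remove this, because the difference in detection would itself be an effect of treatment.

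At stake is the reading of the endpoint. A pooled rate ratio below 1 could mean fewer infections, or the same number of infections with fewer triggered swabs. No planned analysis tells these apart. SAP 9.6.1 and 9.6.2 use mid-turbinate results only to confirm CSRIs. Otherwise the scheduled-swab results appear only in a listing (16.2.6.2.2).

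**Working it through.** **The plan's figures.** The documents state no design figure for this endpoint. The trial's sample size does reproduce: a likelihood-ratio chi-square test at 28.2% versus 19.7% with 533 per arm has power 0.903, against the stated 90%. Only the 533 per arm is used below, in step 4.

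**Inputs from the documents.** Scheduled swabs at nominal Days 14, 28, 42, 56, 84 and 112. Counting window Day 3 to Day 112, which is 109 days.

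**Assumed inputs (not in the documents).** Detectable shedding d of 5 to 14 days. Share s of placebo infections meeting the trigger, 30% to 70%. Share f of those pushed below the trigger by the drug, 30%. Triggered swabs catch 90% of triggered infections. Onset uniform over the window. Equal true infection rates and equal shedding in both arms.

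**Step 1: chance q that a scheduled swab catches an infection.** This is the part of the window lying within d days before a swab, divided by 109.

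- d = 5: 30/109 = 0.275
- d = 7: 42/109 = 0.385
- d = 10: 60/109 = 0.550
- d = 14: 81/109 = 0.743 (11 days before the first swab, then 5 × 14)

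**Step 2: expected pooled rate ratio, each infection counted once.** A triggered infection is detected with probability D = 1 − 0.1(1 − q); any other with probability q.

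Ratio = [0.7sD + (1 − 0.7s)q] / [sD + (1 − s)q]

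Worked case, d = 7 and s = 0.5: D = 1 − 0.1 × 0.615 = 0.9385. The numerator is 0.35 × 0.9385 + 0.65 × 0.385 = 0.579. The denominator is 0.5 × 0.9385 + 0.5 × 0.385 = 0.662. The ratio is 0.87, although no infection was prevented. The denominator also shows that 66% of placebo infections are captured.

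| d (days) | Ratio at s = 0.7 | Ratio at s = 0.3 |
|---|---|---|
| 5 | 0.81 | 0.88 |
| 7 | 0.85 | 0.91 |
| 10 | 0.90 | 0.95 |
| 14 | 0.95 | 0.97 |

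Over the same grid, the placebo rate of all infections is understated by about 10% (d = 14, s = 0.7) to 53% (d = 5, s = 0.3).

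**Step 3: variations.**

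- Triggered swabs catch every triggered infection, s = 0.6: 0.82, 0.85, 0.90 and 0.95 for d = 5, 7, 10 and 14.
- Every positive specimen counted, as 9.5.1 is worded, with s = 0.6 and full capture: ratio = (q + 0.7s)/(q + s), giving 0.79, 0.82, 0.84 and 0.87. For d = 5 this is 0.695/0.875.
- f = 0, meaning infections are milder but still reported on two entries: 1.00 throughout.

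**Step 4: nominal significance.** This also assumes dispersion 0.5 and 0.4 to 1.0 infections per subject. With 533 per arm, s = 0.6, f = 0.3 and full capture, a normal approximation gives these chances of a nominally significant result favouring the drug: 25% to 46% at d = 7, 14% to 25% at d = 10, and 7% to 10% at d = 14.

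**Step 5: scheduled swabs alone.** With d no more than 14 days, each infection contributes on average q positive scheduled swabs in either arm, whatever its symptoms. The expected ratio is q/q = 1.00, provided the drug does not change shedding duration.

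The offset appears in none of these ratios. The bias sits in the numerator; the offset only treats all exposure time as if it were observed.

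**The case against.** Several points on the other side stand.

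- **Milder illness alone.** A reader might infer that any drug that makes infections milder would appear to prevent them. The documents do not support that. The trigger has no severity threshold, and 9.5.1 counts positives outside CSRIs. The first paragraph of 9.5.1 does describe the triggered specimens as taken during CSRI episodes. Applied restrictively, that would make severity matter, but the second paragraph overrides it.
- **The 30% effect.** A reader might carry over the planned 30% reduction in CSRI. CSRI requires at least two symptoms of moderate or greater severity, so a 30% reduction could leave triggered swabbing unchanged. The 30% in the working is an assumption of its own.
- **The time denominator.** A reader might blame the exposure offset. Changing it alone would leave the ratio as it is.
- **Size.** The larger error rates need many infections per subject. At dispersion 0.5, 28.2% CSRI incidence implies about 0.36 CSRIs per placebo subject, from (1 + 0.5μ)^(−2) = 0.718. One infection per subject with 60% triggered would be 0.6, so much of the excess would be illness short of a CSRI. At 14 days of shedding the effect is small.
- **Replacing the endpoint.** The protocol defines it as pooled. Detections per swab measure prevalence, and would fall if the drug shortened shedding. That is a good reason not to replace the pooled rate.

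None of this removes the central point. Detection depends on symptoms, and no planned analysis is free of that dependence.

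**Conclusion.** The point holds as an interpretive weakness in an exploratory endpoint. If the drug moves some infections below the swab trigger, and detectable shedding is shorter than the gaps between visits, the pooled rate ratio is biased below 1. The direction follows from the documents' sampling rules. The size rests on assumed inputs: about 0.81 to 0.97 over the grid above with each infection counted once, further from 1 if every positive specimen counts, and exactly 1.00 if no infection crosses the trigger.

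A reader might take this as a threat to the trial's main conclusions. It is not one. The endpoint lies outside the H1 to H9 sequence, so the primary result and the study-wise error rate are untouched. Nor do the documents plan a formal claim of prevention from it. What is affected is any statement that RTB101 reduces infection irrespective of symptoms, which is the question Protocol 3.2 gives this endpoint to answer.

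**What to change.** Keep the pooled rate as the protocol defines it, and make two additions to SAP 9.5.1.

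1. Prespecify an analysis of virus-positive scheduled mid-turbinate swabs at Weeks 2 to 16 only. Use the 9.4.2 model and covariates, with log(number of post-baseline scheduled swabs with a result) as the offset. Report it as detections per swab.
2. State that the pooled rate depends on symptom-triggered sampling, and that it will not be read as an effect on infection irrespective of symptoms unless the scheduled-swab analysis agrees.

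The cost is SAP wording and one extra exploratory table from swabs already being collected. The added analysis has fewer events and so less precision, and its measure also reflects how long shedding lasts; the SAP should say so beside it.

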- Obtain information about whether subjects have been evaluated in an ER or urgent care facility or been admitted to a hospital or skilled nursing facility since their last visit.
- Blood and urine samples will be obtained for safety assessments.
- A mid-turbinate swab will be obtained. If a subject presents with respiratory illness symptoms at this visit they may also have a nasopharyngeal swab, RIDT and sputum sample (if applicable) obtained as outlined in the unscheduled visit assessments.
- Remaining study drug brought back by the subject to the study visit will be counted to ensure compliance and subject will be retrained if compliance is not 100%. Subject will be re-dispensed the same study drug that they brought to the visit.
- Those subjects participating in the PK assessments (per the IXRS randomization) will be asked to not take study drug on the morning of their next scheduled study visit (Week 4 [or Week 6 if applicable]) as the subject will be administered study drug together with a light meal at the study site.

Week 4 Visit:

The following evaluations will be performed:

- Review of interim and current medical (including cardiac) conditions (see SOM for details).
- Clinical evaluation, including a targeted physical exam to include measurements of weight, blood pressure, heart rate, respiratory rate, and temperature, and an exam of the lungs, heart, oral cavity, and skin.
- ECG for safety monitoring.
- Assessments for safety including any adverse/serious adverse events and any concomitant medications taken since the last study visit.
- Obtain information about whether subjects have been evaluated in an ER or urgent care facility or been admitted to a hospital or skilled nursing facility since their last visit.
- Blood and urine will be obtained for safety assessments.
- A mid-turbinate swab will be obtained. If a subject presents with respiratory illness symptoms at this visit they may also have a nasopharyngeal swab, RIDT and sputum sample (if applicable) obtained as outlined in the unscheduled visit assessments.
- PK and biomarker assessments (only for those subjects identified per the IXRS randomization for PK assessments):
 - A pre-dose PK sample will be taken after which study drug will be administered at the study site together with a light meal.
 - The remaining PK samples will be drawn at the following timepoints post study drug administration:
 - 30 minutes (± 10 minutes)
 - 1 hour (± 15 minutes)
 - 2 hour (± 30 minutes)

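### SAP 9.5.1 defines a rate of viral infections but counts positive specimens, with no rule for merging repeat positives or removing Baseline carriage

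*SAP*

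**What the plan says.** SAP 9.5.1 has two sentences that matter.

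- The first gives the endpoint: "The rate of all laboratory-confirmed viral infections with or without symptoms beginning at least 3 days after the start of study drug treatment". The unit is an infection, dated by when it begins.
- The second gives the count. It starts from "All positive results from specimens (respiratory pathogen PCR of nasopharyngeal swabs or midturbinate swabs and/or RIDT") and says that each of these "will count as laboratory-confirmed viral infections (both symptomatic and asymptomatic"), provided that the specimen falls in the same time window. The unit is now a positive result, dated by specimen collection.

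The sampling schedule is dense enough for the difference to matter. Protocol 3.1 (Weeks 2-12 Visits) says "Subjects will also have a mid-turbinate swab taken at each visit regardless of whether the subject reports respiratory illness symptoms". Section 6 has subjects return "every 2 weeks (Visits Week 2, 4, 6, and 8) for the first 8 weeks, and then every 4 weeks (Visits Week 12 and 16"), and Week 16 also has a swab, so there are six scheduled post-Baseline swabs. At Baseline, Section 6 adds "A mid-turbinate swab will be obtained". For a subject with symptoms at a scheduled visit, Section 6 says "they may also have a nasopharyngeal swab, RIDT and sputum sample (if applicable) obtained as outlined in the unscheduled visit assessments".

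The analysis method is borrowed from SAP 9.4.2: negative binomial regression with an offset for length of exposure.

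**The concern.** Three kinds of over-count follow from the literal rule.

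1. **Several specimens for one illness.** A nasopharyngeal positive and a mid-turbinate positive for the same virus are two counts. In influenza-like illness, a positive RIDT is a third.
2. **Repeat positives at scheduled visits.** A virus still detectable at the next visit is counted again.
3. **Carriage from before treatment.** The Day 0 positive falls outside the window. If the same virus is still found at Week 2, that specimen qualifies, although the infection did not begin on treatment.

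Protocol 3.2 gives the endpoint the purpose of assessing antiviral effect. A ratio of positive specimens is a ratio of incidence multiplied by positives per infection. A drug that only speeds clearance would lower it, and a reader could report that as fewer infections.

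**Working it through.** **Is there a merging rule elsewhere?** I found none that reaches this endpoint.

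| Place | What it does | Applies to 9.5.1? |
|---|---|---|
| SAP 7.2.1 | Merges symptoms into one CSRI until 7 symptom-free entries | CSRIs only |
| SAP 9.4.1 | Several positives confirm one CSRI | CSRIs only |
| SAP 9.4.2 | Offset | Corrects for exposure length, not duplicates |
| Protocol Table 6-1 note 14 and 6.7.2 | One nasopharyngeal swab per episode | Limits nasopharyngeal repeats only |
| Protocol 6.7.2 | RIDT for influenza-like illness | Narrows same-day triple counts |
| Protocol 4.2, exclusion 7 | Recent RTI, by history and judgement | Does not catch silent carriers |

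**The plan's own figure.** None is given for this endpoint. The only power statement is for the primary endpoint: 28.2% against 19.7%, 1066 subjects, 90% power. The pooled two-proportion formula gives 528 per arm (1056 in total), and likelihood-ratio chi-square power at 533 per arm is 0.903. That figure reproduces and does not depend on this point.

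**Mid-turbinate swabs alone.** Inputs from the documents: swabs on days 14, 28, 42, 56, 84 and 112, and onset from day 3 to day 112 (109 days). Assumptions: uniform onset, fixed shedding time D, and perfect sensitivity while shedding. A swab on day v is positive if onset falls in the D days before it, cut off at day 3. Positives per infection are the sum of those window lengths divided by 109. Detected infections are the length of their union divided by 109.

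| D (days) | Sum of windows | Positives per infection | Union | Detected per infection |
|---|---|---|---|---|
| 10 | 6×10 = 60 | 0.55 | 60 | 0.55 |
| 14 | 11 + 5×14 = 81 | 0.74 | 81 | 0.74 |
| 21 | 11 + 5×21 = 116 | 1.06 | 53 + 21 + 21 = 95 | 0.87 |
| 28 | 11 + 25 + 4×28 = 148 | 1.36 | 109 | 1.00 |

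Repeat mid-turbinate counts therefore appear only once shedding exceeds 14 days (28 days after Week 8).

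**Adding symptomatic swabs.** Assume that a share s = 0.5 of infections also has one positive nasopharyngeal swab. Counts are s + positives, and distinct infections are s + (1 − s) × detected.

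- D = 14: (0.5 + 0.743)/(0.5 + 0.5×0.743) = 1.243/0.872 = 1.43
- D = 21: (0.5 + 1.064)/(0.5 + 0.5×0.872) = 1.564/0.936 = 1.67
- D = 28: (0.5 + 1.358)/(0.5 + 0.5×1.000) = 1.858/1.000 = 1.86

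Varying s from 0.3 to 0.7, with an RIDT positive in 0 to 20% of those, widens this to about 1.3 to 2.2. Simulation with exponential shedding (mean 10 to 21 days, s = 0.5) gives about 1.4 to 1.8.

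**Rate ratio when the drug prevents nothing and only shortens shedding** (mid-turbinate swabs alone, same incidence in both arms):

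| Shedding, placebo to active (days) | All positives | Distinct infections |
|---|---|---|
| 14 to 10 | 60/81 = 0.74 | 60/81 = 0.74 |
| 21 to 14 | 81/116 = 0.70 | 81/95 = 0.85 |
| 28 to 14 | 81/148 = 0.55 | 81/109 = 0.74 |

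With symptomatic swabs at s = 0.5, the 21-to-14 case is 1.243/1.564 = 0.79 against 0.872/0.936 = 0.93. In simulations with 25% shorter exponential shedding, the specimen ratio is 0.81 to 0.88 and the distinct-infection ratio 0.86 to 0.95, depending on mean shedding and on a delay of 0 to 4 days to the symptomatic swab.

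**Baseline carriers.** If remaining shedding is uniform on 0 to D, the chance of a positive at Week 2 is (D − 14)/D when D exceeds 14: zero at D = 14, 7/21 = 0.33 at D = 21, and 14/28 = 0.50 at D = 28.

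**The case against.** The strongest reply is that the second sentence of 9.5.1 only lists which results are eligible, with or without a CSRI, and that the first sentence still governs. A virus carried from Baseline then did not begin on treatment, and a repeat positive is not a new infection. This reading is possible, so a reader who infers that the plan certainly counts every positive goes further than the text allows. It does not rescue the section: the episode rule is then undefined rather than wrong, and the same text is needed.

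Other points stand in part:

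- **Same-day duplication is narrower than it looks.** Extra tests at a scheduled visit are optional, nasopharyngeal swabs are limited to one per episode, and RIDT is for influenza-like illness. Three counts for one virus on one day needs influenza. Two counts do not.
- **Every magnitude is assumed.** Much of the 1.4 to 1.8 comes from pairing a symptomatic swab with a scheduled one. With fixed shedding of 14 days or less, mid-turbinate swabs alone give no inflation.
- **Randomisation protects some comparisons.** If the drug affects neither incidence nor shedding, both arms are inflated alike. If it affects only incidence, the ratio for new infections is unchanged. The distortion needs an effect on shedding, which an antiviral mechanism makes plausible but which the documents do not quantify.
- **Shorter shedding is arguably an antiviral effect.** That is fair, but it is not a lower rate of infections, which is how the endpoint is named.
- **SAP 9.6.1 and 9.6.2 already use mid-turbinate swabs at CSRI level.** They cover symptomatic illness only.

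**Conclusion.** The inconsistency in SAP 9.5.1 is on the page and needs no assumption. What rests on assumption is its size: roughly 1.4 to 1.8 positive specimens per distinct detected infection for mean shedding of 10 to 21 days with half of infections also swabbed for symptoms, and wider for other inputs.

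Two stronger conclusions are tempting and not supported. First, a reader might infer that counting distinct infections would give a clean measure of prevention. It would not: swabs 14 to 28 days apart miss short infections more often, so the corrected ratio still falls below 1 when nothing is prevented, and in the 14-to-10-day case it does not improve at all. Second, a reader might infer a threat to the trial's main conclusions. The endpoint is exploratory and outside the H1 to H9 sequence, so the primary result, sample size and study-wise error control are untouched. The consequence is confined to how the antiviral effect is described. The change is worth making, but the trial does not hinge on it.

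**What to change.** Before unblinding, replace the counting sentence in SAP 9.5.1 with an episode rule:

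- Count distinct infections by virus. Different viruses count separately.
- Merge same-virus positives that share a date, fall within one CSRI, or lie on consecutive specimens with no intervening negative.
- If a maximum interval is also used, keep it clear of the visit gap. With a window of ±5 days at each visit, a nominal 28-day gap can run from 28 − 10 = 18 to 28 + 10 = 38 days, so a 28-day limit would let scheduling decide. A limit above 38 days, such as 42, avoids this for adjacent scheduled visits. Report sensitivity values on either side, for example 28 days and no limit.
- Do not count a virus positive on the Day 0 swab until a later negative swab.
- Restrict the count to viral targets. Protocol 6.7.4 describes a panel with 17 viral and 3 bacterial pathogens, and the present wording does not exclude the latter.
- State in the SAP and report that the distinct-infection ratio still partly reflects shedding duration.

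The cost is SAP text and programming on swabs already collected. The maximum interval is a convention, so it should be fixed in advance: an episode rule chosen after unblinding would itself be open to challenge.
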